2.1.3.5 Other efficacy endpoints

2.1.3.5.1 TTP-related events

TTP related event is defined as:

- TTP-related death,
- recurrence of TTP
- or reported major thromboembolic event [e.g., myocardial infarction, cerebrovascular accident, pulmonary embolism or deep venous thrombosis] based on SMQ based on the SMQ ‘Embolic and thrombotic events (arterial, venous, and vessel type unspecified and mixed arterial and venous)’.

2.1.3.5.2 Time to TTP-related events:

The time to TTP related event (in days) is defined as the date from screening/baseline visit to the date of the first TTP related event. Patients without an event during the ALX0681-C302 study are censored at the end of the study.

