2.1.3.5.5 Time to first recurrence of aTTP

The event of interest is the first recurrence of aTTP experienced by the patients in the ALX681-C302 study. Time to first recurrence (in days) is defined as the date from end of previous aTTP episode in the ALX0681-C301 study to the date of the event. Patients without an aTTP recurrence during the ALX0681-C302 study are censored at the end of the study. This endpoint is only computed for subjects who did not have any recurrence in the ALX0681-C301, or between the end of ALX0681-C301 trial and the beginning of the ALX-0681C302 trial.

2.1.3.5.6 Time to major thromboembolic events:

The time to the first major thromboembolic event (in days) is defined as the date from screening/baseline visit to the date of the first thromboembolic event. Patient without a thromboembolic event are censored at the end of the study.

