2.4.4.2 Major thromboembolic events

The number and percentage of participants with a major thromboembolic event as well as the number of such events, will be summarized. The total number and percentage of participants who have at least one of major thromboembolic event will also be calculated. Within the major thromboembolic events category, the frequency tabulation of PTs will also be summarized.

For the ITO population, it will be after 12M FU, 24M FU and 36M FU as well as a cumulative summary. For the Recurrence population, it will be during each recurrence period separately.

The time to the first major thromboembolic event will be summarized on the ITO population, using Kaplan-Meier (KM) estimates such as the median, 25% percentile and 75% percentile with associated 95% CIs, as well as the number of events and the number of censored observations. The KM estimates will also be presented graphically.

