2.4.5 Analyses of safety data

The summary of safety results will be presented by treatment group. For the ITO population, the treatment groups are:

- Caplacizumab total: Subjects who received caplacizumab during the ALX0681-C301 study (during the double blind or the open-label periods).
- Not treated: Subjects who never received Caplacizumab during the ALX0681-C301 trial

For the recurrence population, adverse events will be presented for:

- Treated with IMP: patients treated with caplacizumab in the ALX0681-C302 study
- Not Treated with IMP: patients not treated with caplacizumab in the ALX0681-C302 study during the trial

General common rules

All safety analyses will be performed on the ITO and recurrence populations as defined in [Section 2.3.2](#), unless otherwise specified, using the following common rules:

- For analysis related to the Q6M FU visits, the baseline value is defined as screening/baseline value visit. For analysis related to the recurrence period, the baseline value is defined as the recurrence visit value and will be calculated for each recurrence period separately
- For assessments with multiple parameters per participant (such as laboratory assessments), baseline will be determined per parameter individually. It is recognized that baseline assessments may thus come from more than one assessment and not just from the “baseline visit” assessment.
- For quantitative safety parameters based on central laboratory/reading measurements, descriptive statistics will be used to summarize results and change from baseline values by visit.
- The analysis of the safety variables will be essentially descriptive, and no systematic testing is planned.

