When cross-tabulating AE PTs versus an AE attribute (e.g., severity), the worst-case is always applied within each analysis period. This means that when a participant has the same AE PT twice in the same analysis period, then the participant is reported only once: with the worst severity. If this happens in two different analysis periods, the participant is reported twice: once in each analysis period.

AE onset day and AE duration are defined as follows:

- AE onset day
 - AE start date – reference date + 1 day (when the AE start date is completely known)
 - Missing (when the AE start date is incomplete or unknown).
 - Two different onset days will be calculated: one with the reference date being the screening/baseline visit; and the other, for adverse events occurring during the recurrence period, with reference date being the recurrence visit.
- AE duration
 - AE stop date – AE start date + 1 day (when both dates are completely known)

- Trial termination date – AE start date + 1 day (when the AE start date is fully known but the AE is not resolved at the end of the trial): in this case the duration will be presented as “>x days” in the listing rather than “x days”
- Missing (when the AE start date is incomplete or unknown, or when the AE has resolved but with an incomplete or unknown end date).

These derived parameters will only be presented in the listings. Note that the start and stop times of the AE are not used.

AE incidence tables will present by SOC and PT, sorted by decreasing frequency of SOC and PTs within SOCs, the number (n) and percentage (%) of participants experiencing an adverse event. The denominator for computation of percentages is the population within each treatment group.

The following analysis periods will be considered for all TEAEs tables on the recurrence population:

- Treatment daily PE period
- Treatment post-daily PE period
- Overall treatment period
- Follow-up period
- Overall recurrence period

The following analysis periods will be considered for AE occurring in the recurrence periods for patients not treated with the IMP:

- Daily PE period
- Post Daily PE period
- Overall recurrence period

The following analysis period will be considered for the adverse events observed during the study for the ITO population:

- Overall study period

Analysis of all adverse events

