The following adverse event summaries will be generated by analysis period for the patients not treated in the recurrence population and for the ITO population.

- Overview of adverse events, summarizing number (%) of participants, the number of events, and the incidence per 100 person months, which will be calculated as: $100 \times (\text{Number of participants with AE}) / (\text{Total number of months observed within analysis period, summed for all participants})$ with any
 - Participants with at least one AE
 - Participants with at least one serious AE

- Participants with at least one AE leading to death
- Participants with at least one PE-related AE (only for the recurrence population)
- Participants with at least one serious PE-related AE (only for the recurrence population)
- Participants with at least one bleeding event, i.e. an event documented as event indicating an increased bleeding tendency
- Participants with at least one bleeding event, based on the Standardized MedDRA Query (SMQ) “Haemorrhage” with exclusion of the PT “TTP”
- Participants with at least one thromboembolic event, based on the SMQ “Embolic and thrombotic events” (arterial, venous, and vessel type unspecified and mixed arterial and venous) with exclusion of the PT “TTP”
- All AE by primary SOC and PT, showing the number (%) of participants with at least 1 AE. The number of events and the number and percentage of participants having an event will be presented.
- AEs will be summarized by SOC, PT and severity. This will be done for each analysis period. The number and percentage of participants having an event will be presented for the worst severity reported for each event.

Analysis of all treatment-emergent adverse events

The following treatment-emergent adverse event summaries will be generated by analysis period for the recurrence population.

- Overview of treatment-emergent adverse events, summarizing number (%) of participants, the number of events, and the incidence per 100 person months, which will be calculated as: $100 \times (\text{Number of participants with AE}) / (\text{Total number of months observed within analysis period, summed for all participants})$ with any
 - Participants with at least one TEAE
 - Participants with at least one serious TEAE
 - Participants with at least one TEAE leading to death
 - Participants with at least one TEAE for which the study drug was interrupted
 - Participants with at least one TEAE for which the study drug was withdrawn

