- Serious (TE)AEs considered treatment-related by the investigator will be summarized by SOC and PT. This will be done for each analysis period. The number of events and the number and percentage of participants having an event will be presented.

Analysis of all treatment-emergent adverse event(s) leading to treatment discontinuation

- TEAEs leading to discontinuation will be summarized separately and combined by SOC and PT. This will be done for each analysis period. The number of events and the number and percentage of participants having an event will be presented.

Thromboembolic events

- Thromboembolic events (treatment-emergent or not), based on the SMQ “Embolic and thrombotic events” (arterial, venous, and vessel type unspecified and mixed arterial and venous) with exclusion of the PT “TTP”, will be summarized by SOC and PT. This will be

done for each analysis period and population. The number of events and the number and percentage of participants having an event will be presented.

Bleeding events

- Bleeding events and serious bleeding events (treatment-emergent or not) will be summarized by SOC and PT. This will be done for each analysis period. The number of events and the number and percentage of participants having an event will be presented based on eCRF and SMQ.
- Treatment-emergent bleeding events based on SMQ and bleeding events considered treatment-related by the investigator based on eCRF will be summarized by SOC, PT and severity. This will be done for each analysis period. The number of events and the number and percentage of participants having an event will be presented for the worst severity reported for each event based on the eCRF and SMQ separately.

Hypersensitivity reactions

- Hypersensitivity reactions (including anaphylaxis and angioedema) will be summarized by SOC and PT. This will be done for each analysis period. The number of events and the number and percentage of participants having an event will be presented. This analysis will be repeated for hypersensitivity reactions considered treatment-related by the investigator.

Listings

- Listings will be provided for all AE, SAE, TEAE leading to treatment discontinuation, bleeding events, severe/serious hypersensitivity AE.

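### The efficacy definition of major thromboembolic event keeps the PT TTP that every safety analysis of the same SMQ removes, so a recurrence coded to that PT would count under both endpoints

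*SAP*

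**What the plan says.** SAP 2.1.3.5.1 defines a TTP-related event as TTP-related death, recurrence of TTP, or a reported major thromboembolic event. The last component is identified by the SMQ "Embolic and thrombotic events (arterial, venous, and vessel type unspecified and mixed arterial and venous"), with a few clinical examples and no excluded term. SAP 2.1.3.5.6 builds the time-to-event endpoint on it: the time "is defined as the date from screening/baseline visit to the date of the first thromboembolic event". SAP 2.4.4.2 analyses it: "The time to the first major thromboembolic event will be summarized on the ITO population, using Kaplan-Meier (KM) estimates". Neither section adds an exclusion or a different definition.

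The safety sections use the same SMQ. In the overviews of adverse events and of treatment-emergent adverse events in SAP 2.4.5.1, the SMQ is given as "vessel type unspecified and mixed arterial and venous) with exclusion of the PT" TTP. The dedicated table in that section, "Thromboembolic events (treatment-emergent or not), based on the SMQ", carries the same exclusion and is to be "done for each analysis period and population".

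The protocol synopsis (Main Endpoints) lists recurrence of disease and major thromboembolic events as separate endpoints, each with a proportion, a number of events and a time to event. Protocol 3.6.4 describes the thromboembolic endpoint by examples only and names no SMQ.

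**The concern.** Protocol 3.4.9.1 and 3.5.2 require every exacerbation and relapse to be reported as a serious adverse event, and SAP 2.1.4.1 codes every such event to a PT. A recurrence coded to the PT TTP would therefore meet the efficacy definition of a major thromboembolic event. The authors evidently saw that this term needs removing from SMQ-based counts, because they removed it from each safety analysis. SAP 1.6, which lists the statistical modifications, gives no reason for treating efficacy differently.

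What is at stake is the stand-alone thromboembolic endpoint in the total population: its proportion, event count and Kaplan-Meier curve, and its summaries by recurrence period. These would partly repeat the recurrence endpoint, and the study report could show two unreconciled thromboembolic counts from one SMQ in one population.

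There are two related gaps. SAP 2.4.4.1 does not say whether one episode can add twice to the number of TTP-related events. It also summarises the composite, which includes recurrence, within each recurrence period of a population selected for having a recurrence. Every subject meets it if the qualifying recurrence counts.

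**Working it through.** **1. The definitions side by side**

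| Analysis | Source | PT TTP removed? |
|---|---|---|
| Efficacy definition | SAP 2.1.3.5.1 | No |
| Time to first event | SAP 2.1.3.5.6 | No |
| Efficacy summary and Kaplan-Meier curve | SAP 2.4.4.2 | No |
| Adverse event overview | SAP 2.4.5.1 | Yes |
| Treatment-emergent overview | SAP 2.4.5.1 | Yes |
| Thromboembolic events by SOC and PT | SAP 2.4.5.1 | Yes |

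**2. Can the SMQ capture a TTP episode?** Protocol 1.2.4 reports a Phase II analysis of treatment-emergent events with this SMQ (safety population: 35 caplacizumab, 37 placebo).

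- The stated figures reproduce. Caplacizumab: 4/35 = 11.4%. Placebo: (14 + 2)/37 = 16/37 = 43.2%, if the two deaths were not among the 14 subjects with an event.
- Event totals agree: 1 + 3 = 4 and 2 + 1 + 1 + 1 + 1 + 1 + 13 = 20.
- TTP exacerbations: (3 + 13)/(4 + 20) = 16/24 = 67%.
- Without them, caplacizumab goes from 4/35 (11.4%) to 1/35 (2.9%).
- Placebo goes from 14/37 (37.8%) to at most 7/37 (18.9%), because 20 − 13 = 7 events remain. The same protocol section gives 11 placebo subjects with an exacerbation. If the 13 events occurred in those 11, at least 14 − 11 = 3 subjects had another event (3/37 = 8.1%). If they were spread over 13 subjects, the floor is 14 − 13 = 1 (1/37 = 2.7%).

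So the SMQ can capture TTP episodes.

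**3. Which outputs change?**

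- *Thromboembolic endpoint, total population:* proportion, count and curve all change if any recurrence is coded to the PT.
- *Thromboembolic events by recurrence period:* these change in the same way.
- *Composite, proportion and time to first event:* essentially unchanged, since recurrence is already a component.
- *Composite, number of events:* double counting arises only if component counts are summed, which SAP 2.4.4.1 does not say.
- *Group-wise summaries:* undetermined. SAP 2.4.4 follows subjects up to their first recurrence but does not say whether the adverse event for that recurrence falls inside the window.

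**4. Illustration, not an estimate.** Let p be the proportion with a non-TTP thromboembolic event (assumed 5%, independent of recurrence). Let r be the proportion with a recurrence, and c the share of those subjects with at least one recurrence coded to the PT (assumed). The reported proportion is 1 − (1 − p)(1 − rc).

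| r (Protocol 1.1) | c = 0 | c = 0.5 | c = 1 |
|---|---|---|---|
| 18% (median) | 5.0% | 1 − 0.95 × 0.91 = 13.6% | 1 − 0.95 × 0.82 = 22.1% |
| 3% (lowest) | 5.0% | 1 − 0.95 × 0.985 = 6.4% | 1 − 0.95 × 0.97 = 7.9% |

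With p from 2% to 10% and c = 1, the range is 19.6% to 26.2% at r = 18%, and 4.9% to 12.7% at r = 3%. The 18% is a literature median among patients followed for at least six months, not a three-year figure for this study.

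**The case against.** The strongest reply is that the plan already lets a reader see the problem. SAP 2.4.4.2 tabulates PTs within the thromboembolic category, so any TTP terms would be visible. SAP 2.4.5.1 plans a TTP-excluded count for the total study: "The following analysis period will be considered for the adverse events observed during the study for the ITO population" is the overall study period. Nothing is formally tested (SAP 2.4.4.8), so no error rate or power is affected. All of this is true, but it does not repair the endpoint. The safety version has no 12- or 24-month cuts and no Kaplan-Meier curve. It also uses different groups: "The summary of safety results will be presented by treatment group", meaning receipt of caplacizumab in the parent study rather than the randomised arm.

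A second reply is that the word *major* and the listed examples imply a narrower clinical meaning. The examples are only illustrative, the operational rule is the SMQ, and the Phase II analysis also said *major* and still counted exacerbations.

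A third reply stands in full. A reader might infer from Phase II that about two thirds of the thromboembolic events here would be recurrences. The documents do not support that. The Phase II count was limited to treatment-emergent events. In that study 13 caplacizumab subjects had an exacerbation and/or relapse and 3 had an exacerbation, so at least 10 had a relapse only; yet the SMQ count for that arm names 3 exacerbations and no relapse. Whether timing or coding kept relapses out is not stated. A subject's first recurrence in the present study occurs off study drug.

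**Conclusion.** The definitional mismatch is certain on the text and should be fixed. Its effect is conditional: it occurs only to the extent that recurrences are coded to the PT TTP, and the documents do not say how they are coded. That this PT belongs to the SMQ is inferred from the SAP's own exclusions and from the Phase II counts.

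If some recurrences are so coded, the thromboembolic proportion, event count and Kaplan-Meier curve in the total population are inflated by recurrence, as are the recurrence-period summaries, and they disagree with the safety table. Under the stated assumptions a 5% proportion could be reported as anything from 5% (no such coding) to 22.1% (all such coding, 18% recurrence).

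Two stronger readings should be resisted. One is that the composite TTP-related endpoint is invalid: its proportion and time to first event barely move. The other is that the comparison of the former randomised groups is distorted, or alternatively is safe: the SAP does not settle either, because the follow-up window at first recurrence is not defined closely enough.

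**What to change.** - In SAP 2.1.3.5.1, 2.1.3.5.6 and 2.4.4.2, exclude the PT TTP from the SMQ, as SAP 2.4.5.1 already does.
- In SAP 2.4.4.1, state that one episode counts once in the number of TTP-related events.
- In SAP 2.4.4.1, for the recurrence population, do not let the recurrence that qualifies the subject for the period satisfy the composite by itself. Still count TTP-related death, thromboembolic events (PT TTP excluded), and any new recurrence during an ongoing recurrence period. That new recurrence should be an event of the earlier period. Protocol 3.1.1, 3.3.1 and 3.4.1.3 start a new visit cycle for it, so it could otherwise be treated as the opening of a new period and be counted in neither.

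The cost is SAP wording and one term filter already specified for the safety tables. No new data are needed. The reported thromboembolic count may fall.

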2.1.3.5.3 Death

Adverse event with a fatal outcome.

2.1.3.5.4 Recurrence of aTTP

A recurrence of aTTP is defined as recurrent thrombocytopenia requiring initiation of daily plasma exchange (PE).

2.1.3.5.5 Time to first recurrence of aTTP

The event of interest is the first recurrence of aTTP experienced by the patients in the ALX681-C302 study. Time to first recurrence (in days) is defined as the date from end of previous aTTP episode in the ALX0681-C301 study to the date of the event. Patients without an aTTP recurrence during the ALX0681-C302 study are censored at the end of the study. This endpoint is only computed for subjects who did not have any recurrence in the ALX0681-C301, or between the end of ALX0681-C301 trial and the beginning of the ALX-0681C302 trial.

2.1.3.5.6 Time to major thromboembolic events:

The time to the first major thromboembolic event (in days) is defined as the date from screening/baseline visit to the date of the first thromboembolic event. Patient without a thromboembolic event are censored at the end of the study.

